Official Title of the Study	Investigation of the Role of Steroids in Enhancing Voice Therapy Outcomes
NCT Number	NCT02286960
Study ID	13-00096
Version Date	June 19, 2013

S13-00096: Investigation of the Role of Steroids in Enhancing Voice Therapy Outcomes RESEARCH PROTOCOL (version 6.19.13)

SPECIFIC AIMS

The recently-published clinical practice guidelines (CPG) for hoarseness (1) pointed out several significant deficiencies in the laryngology literature. **One of the more confounding statements in the document was related to the paucity of evidence for the use of steroids for the treatment of patients with complaints of hoarseness, regardless of etiology.** Specifically, the document only suggests a role for steroids in the context of 'allergic laryngitis' in vocal performers. To address this comment, we recently surveyed the greater otolaryngology community in an attempt to describe current practice patterns with regard to the use of steroids for voice disorders (manuscript in revision). The results of this survey confirmed our hypothesis: steroid use is, in fact, quite common among otolaryngologists for a variety of diagnoses underlying voice complaints. Admittedly, these types of surveys are fraught with confounds, but frankly, **this mismatch between the literature and clinical practice presents an opportunity to address this rather large research gap in the study of this very commonly used drug class, one that would benefit from comparative effectiveness research.**

Our anecdotal experience suggests that steroids are effective in improving voice in patients related to the presence of benign vocal fold lesions. Specifically, we commonly use steroids to reduce edema surrounding benign lesions yielding short-term improvement in vocal quality. We also noticed that some patients will have sustained improvement in voice in the long-term following a short course of oral steroids. We hypothesize that these outcomes may be due to a reduction of laryngeal inflammation and phonatory pressures required due to improved glottal closure as well as reduced vocal fold mass, thereby improving the overall laryngeal biomechanics and providing an ideal starting point for behavioral voice therapy.

The current proposal seeks to prospectively and systematically address these phenomena. Typically, patients diagnosed with benign vocal fold lesions are referred for voice therapy for treatment of such lesions that are deemed to be non-surgical cases. Voice therapy has shown benefit for the treatment of a variety of such lesions.(2-10) For the current study, we propose to introduce oral steroids as a variable prior to the initiation of voice therapy. **We hypothesize that subjects in the steroid treatment group will have an enhanced voice therapy experience as evidenced by more rapid improvement, the necessity for fewer voice therapy sessions, and a more global voice improvement when compared to the non-steroid treatment group.**

Specific Aim #1. To determine the effectiveness of a short course of oral steroids prior to the initiation of behavioral voice therapy in patients with benign, phonotraumatic vocal fold lesions.

We hypothesize that a short course of oral steroids with resultant diminished vocal fold edema will increase the efficacy of voice therapy for patients with benign, phonotraumatic lesions. Specifically, we hypothesize that the improved inflammatory profile of the vocal folds will allow for contemporary voice therapy techniques to optimize vocal efficiency with an increased likelihood for long-term translation to everyday scenarios. To address this hypothesis, we seek to perform a prospective, randomized trial to compare objective, subjective, and patient-based outcome measures between two cohorts: patients with benign vocal fold lesions that are assigned to voice therapy that will receive oral steroids immediately prior to the initiation of voice therapy and those who receive no steroids prior to therapy.

Data obtained under the auspices of this mechanism will not only address a significant deficiency in the clinical practice guidelines, but also alter the course of treatment for many patients, potentially yielding a paradigm for optimal patient care.

(a) Significance

Glucocorticoids were first used in the 1940's to treat severe rheumatoid arthritis.(11) The discovery of this class of drugs irreversibly changed the treatment of inflammatory disorders and led to the award of a Nobel prize. Since the initial discovery, steroids have found their way into everyday clinical use for a variety of different disorders. In Otolaryngology, steroids are used in the treatment of facial nerve disorders, chronic sinusitis, and airway disorders, among others.(12-18) Although used commonly for the treatment of voice disorders (unpublished data, manuscript in revision), very little evidence exists for their use.

The clinical practice guidelines (CPG) for hoarseness (1), cites that the only evidence for steroid efficacy in treating vocal fold disease was for allergic laryngitis and for rheumatologic disorders.(19-22) However, in reviewing the citations, it is evident that the “evidence” for use in allergic laryngitis is just expert opinion. Since the publication of the CPG, one publication has reviewed the use of oral steroids in the treatment of patients with vocal fold polyps. In the study, the authors noted that 70.6% patients treated with oral corticosteroids had either complete resolution or shrinkage of vocal fold polyps. However, the retrospective nature of the study and the lack of controls make it difficult to make any definitive conclusions with regards to the true effects of these drugs on vocal fold polyps.

Intralesional steroids have been studied to a greater degree.(23-28) The rationale for their use is based on the high local concentration of drug at the site of injection. In a prospective, multicenter study, Woo, et. al. demonstrated improvement in almost 85% of benign vocal fold lesion cases (Reinke's edema, vocal polyp, nodule, and scarring). In a similar study, Hsu, et. al. found a 91% positive response rate with complete remission in 59% in vocal fold polyp cases treated with intralesional steroid injection.(24) In another prospective study, injected steroids were found to resolve or improve vocal fold nodules in 93% of cases by 4 weeks after treatment.(25) **These studies point to the fact that steroids do have a positive effect on vocal fold pathology, at least when delivered in high doses.**

In our practice and in those at other voice centers, steroids (oral and intralesional) have a wide application in a variety of vocal fold lesions. We have used these drugs orally for the acute treatment of inflammatory conditions of the vocal folds, such as viral laryngitis and vocal fold hemorrhage. We have also used them in an oral form in various other circumstances, including perioperative management of benign vocal fold lesions and for acute and chronic treatment of benign vocal fold lesions. Anecdotally, we have seen value in the use of these drugs orally taken for these indications, though we cannot point to any significant literature base that supports their use. **This is a critical research gap that needs to be addressed.**

(b) Innovation

The current study is innovative, as it will be the first of its kind—one that will prospectively study the efficacy of oral steroids for the treatment of benign vocal fold lesions in a controlled manner. As mentioned above, this is of importance, as these drugs are being used routinely in practice without any evidence base in the literature. Such a study is long overdue.

The current proposal employs a controlled, prospective, randomized, blinded study design. There are many confounding variables in the treatment of vocal fold lesions. For those treated non-surgically, the patients are typically prescribed voice therapy, which includes a range of behavioral modifications and motor learning techniques, along with vocal hygiene measures and education. Since it would be unethical to withhold voice therapy for many of these patients, we chose instead to include it in the study design, as described below.

The current proposal is also innovative in that it will collect several different outcome measures, including objective, subjective, and patient-based outcome measure. The study will allow for quantification of lesion size before and after oral steroid treatment, expert rating of stroboscopy,

subjective rating of vocal quality, and patient rating of voice handicap (Voice Handicap Index-10 or VHI-10 (**see attached questionnaire**)).

In addition, the study will also investigate the potential added advantage of the use of steroids in patients undergoing voice therapy. We hypothesize that oral steroids will lead to a reduction in lesion size, which will substantially aid in the delivery and incorporation of voice therapy techniques, since the reduced lesion size will likely improve glottal closure and reduce vocal fold mass, thereby improving the overall laryngeal biomechanics and providing an ideal starting point for behavioral voice therapy.

(c) Approach

Subjects and Protocol

The specific aim of this project is to determine the effectiveness of a short course of oral steroids prior to the initiation of behavioral voice therapy in patients with benign, phonotraumatic vocal fold lesions. As mentioned above, the study is designed to be prospective, randomized, and controlled. The study group will be recruited from our patient population. Our Center serves the population of the greater metropolitan New York area and has a high volume of patients that present with benign, phonotraumatic vocal fold lesions. Subjects that are non-surgical candidates that are assigned to receive voice therapy at our institution by a single voice therapist ([name]) will be eligible for the study. Potential subjects will be identified by the PI or research staff and will be enrolled right after their clinical visit if they agree to the study protocol and do not meet the exclusion criteria (**Figure 1**). Recruitment will be done solely from the PI's clinical practice. The PI ([name]), research coordinator ([name]) or the co-Investigators ([name], [name]) will be obtaining written consent after their clinical visit. Participants will be provided a copy of the completed consent form. Subjects are free not to participate in the study and their decision will not alter the quality of medical treatment that they will be receiving.

At the time of enrollment, the study coordinator will open a pre-sealed envelope that will assign a subject to either receive oral steroids or placebo prior to the initiation of voice therapy. There will be twenty envelopes each that will read either "steroid" or "placebo". Replacement envelopes will be added if/when subjects drop out from the study.

According to their assignment, subjects will then be dispensed pills and counseled on proper dosing and potential side effects. Subjects assigned to the "steroid" arm will be prescribed two 20 mg prednisone doses per day (40 mg total), taken together in the morning for four days. This dose was chosen as it is the most common dose used in our practice and is within the lower part of the starting range recommended for this drug for the treatment of other inflammatory conditions of the airway, including asthma. A four-day treatment regimen has demonstrated efficacy in our experience, while reducing the risk of side effects.

The therapist ([name]), the scientist that will be conducting the evaluation ([name]) and other individuals involved in collection and analysis of data will be blinded as to whether the subject received drug. The prescribing physician (also the PI) will not be blinded, as this would interfere with routine clinical care of the subject. The research assistant ([name]) will also be non-blinded, as he will be in charge of the randomization and tracking process. Neither of these two individuals will be directly involved in providing or directing therapy, nor will be involved in collection or analysis of the data.

Prior to the initiation of therapy, subjects will be asked to return for an "interval evaluation", which is a research visit. During this evaluation, subjects will undergo videostroboscopy and voice evaluation by one of the co-investigators ([name]). Measures to be collected are described in the following section. Subjects will be reimbursed \$75 for the time and expense involved in returning for this research evaluation, which is considered outside of routine clinical care. The charges for this visit will also be paid by the research account for the same reason.

Subjects will then enter the voice therapy part of the protocol. They will receive an initial evaluation, which is part of routine clinical care. This evaluation will be used to determine the best mode of therapy to pursue. Subjects will receive the form of therapy that specifically meets their needs. The therapist will then keep records of the subject's progress, including a timeline of progress. Subjects will be asked to maintain a regular schedule with the therapist, as this is ideal and will allow for better tracking of time to improvement. During therapy, subjects will be asked to fill out VHI-10 forms on a bi-weekly basis. These forms will be collected for study purposes.

At the completion of therapy, subjects will follow-up with the treating physician ([name]) for a routine follow-up clinical visit. During this visit, routine videostroboscopy and voice evaluation by the co-investigator ([name]) will take place. The general experimental design is summarized in **Figure 2**.

Dependent Variables and Data Collection (Figure 3)

- 1. Voice Handicap Index (VHI)-10.** The primary dependent variable is difference in VHI-10 scores from baseline (pre-treatment). The VHI-10 is a standardized and validated instrument that measures patient perception of their voice disorder.(29) It is administered routinely as a component of clinical care at the NYU Voice Center. Completed forms are scanned into the patient's electronic medical record for easy access and longitudinal comparison. For this study, VHI-10 data will be collected during the initial, interval, and final evaluations.
- 2. Video-Perceptual Analysis.** Videostroboscopic clips will be collected during clinical visits to the NYU Voice Center per normal protocol. Briefly, following application (spray) of topical oxymetazoline and 4% lidocaine, a flexible endoscope will be passed through the nasal cavity and into the pharynx. Subjects will be asked to perform a variety of vocal tasks, including sustained phonation, rapid phonation, sniffing, and counting. Each exam will be recorded as is routine in our practice. There will be a total of three videos collected from each subjects (initial, interval, and final). The images/video obtained will be used for two separate analyses, as described below. For the expert analysis of the videostroboscopy, the clips will be edited in a manner that allows for de-identification and shortening of the clips to demonstrate the most salient parts of the video, including clear imaging of the pathology and at least 5 seconds of continuous mucosal wave. The edited clips will then be sent to 6 expert reviewers (otolaryngologists with a strong laryngology background) for review. The clips will be paired as follows: initial with interval and interval with final. The videos will be presented in random order, followed by a rating form. On the rating form, the reviewers will be asked to rate change in both mucosal wave and glottal closure on a relative 3-point scale (worse, same, better), as described in our previous work.(30) The reviewers will then be asked to return the rating forms, so the data can be collated. Twenty (20) percent of the samples will be repeated randomly for both the expert reviewer and lesion measurement analyses to assess intra-rater reliability. Data will also be subjected to analysis of inter-rater agreement.

The second analysis will be to measure lesion size. This method has been previously described by our group.(30) Briefly, still images of the glottis will be obtained from the video such that the vocal folds are captured in an open position (at least 40 degrees at the anterior commissure). Image J software (NIH) will then be used to outline the lesion and measure the length of the ipsilateral vocal fold (as shown in **Figure 4**). The ratio of these will be used as the adjusted size variable. Measurements will be done bilaterally when appropriate.

- 3. Audio-perceptual Analysis.** Auditory perceptual analysis will be performed based on the protocol recently developed as a component of the Consensus Auditory-Perceptual Evaluation of Voice (CAPE-V). Subjects are asked to repeat pre-determined sentences into a microphone. The stimulus sentences are collected as a component of routine clinical care at the NYU Voice Center and archived permanently via the Computerized Speech Laboratory (KayPentax, Montvale, NJ). These digitized files will then be culled, edited, and presented in random fashion to three expert listeners (speech pathologists with particular expertise in voice who are uninvolved in the current experiment). The standardized CAPE-V forms will be employed using

the visual analog scale. Data will be collected via measurement of the hatch mark on the 100mm line for each variable. Twenty (20) percent of the samples will be repeated randomly to assess intra-rater reliability. Data will also be subjected to analysis inter-rater agreement as well as the overall change from pre-therapy to the two treatment arms.

- 4. Aerodynamic Analysis of Voice.** Aerodynamic analysis of voice will be employed to quantify vocal efficiency (i.e., acoustic output as a function of the pulmonary pressure required to sustain phonation). These measurements are collected as a component of routine patient care at the NYU Voice Center using the Phonatory Airflow System (KayPentax, Montvale, NJ). Essentially, patients are instructed on the appropriate positioning and placement of the mask to ensure no air leakage. Patients are then instructed to produce five productions of /pa/ at their most comfortable pitch and loudness at a rate of approximately 1.5 syllables per second. This protocol is followed at least twice to ensure compliance. The middle three productions will then be subjected to analyses, specifically the variables of average phonatory pressure and dB output will be obtained. This protocol has been described extensively in the literature.(31)

Data Analysis.

In general, data analysis will consist of comparisons of the above collected outcome variables measures from initial to interval evaluations and from interval to final evaluations. Where applicable, we will also conduct comparisons between initial and final evaluations.

Research Versus Non-Research Procedures.

Subjects enrolled in the study will be asked to take either steroid or placebo as described above. Although oral steroids are used regularly in the management of benign vocal fold lesions, in this study we randomize the subjects that will receive steroids versus placebo. This is therefore considered a specific research procedure.

Subjects enrolled in the study will also undergo the data collection procedures described in the section above entitled “Dependent Variables and Data Collection” a total of three times. The initial set of procedures will be performed on the initial visit as a part of the routine clinical care for which the subject is visiting the NYU Voice Center. Similarly, the final study visit is considered part of routine clinical care and the procedures performed will not be performed specifically for research purposes. The procedures performed on the second or interval visit will be considered “research procedures”, since they are being performed outside of routine clinical care. Subjects will be reimbursed for their time and expense in participating in the interval visit and their visit costs will be covered by the study account for this visit as described above. A specific explanation of the procedures that will occur during each visit is provided below (each visit has the same set of procedures):

The patient will complete the Voice Handicap Index (VHI)-10 upon arrival to the clinic. An Audio-perceptual Analysis and an Aerodynamic Analysis of Voice will be performed in the voice lab the speech pathologist ([name] or [name]). Finally, the patient will be brought to the examination room, where a history and physical examination will be performed, followed by videostroboscopy.

Investigational Drug Use.

As mentioned, subjects will be randomized to receive prednisone or placebo. Prednisone is a drug product lawfully marketed in the U.S. The investigation is not intended to be reported to the FDA as a well-controlled study in support of a new indication for use and is not intended to be used to support any other significant change in the labeling for the drug. The investigation is not intended to support a significant change in the advertising for the product. The route, dose and indication of the medication will be as per FDA approval. The investigation is conducted in compliance with the requirements for IRB review set forth in 21 CFR Part 56 and with the requirements for informed consent set forth in 21 CFR

Part 50. The investigation is conducted in compliance with 21 CFR 312.7 (regarding promotion and charging for investigational drugs).

Risks/Benefits of Research Procedures.

The procedures involving some level of risk that will be involved in this study are listed in below, along with a description of the potential risks and benefits.

Videolaryngoscopy – As mentioned above, this procedure involves the use of topical nasal sprays and passage of an endoscope. The use of oxymetazoline and lidocaine nasal sprays involves a small risk of self-limited nasal bleeding and an extremely low risk of an allergic reaction. The benefit of their use is that they minimize the discomfort of the endoscope. The risks of the endoscope include minor nasal discomfort, self-limited nasal bleeding, and gagging. Vasovagal reactions do occur, but are extremely rare. There is no particular benefit to the use of the endoscope, except to help guide diagnosis and therapy clinically.

Steroids – As mentioned above, half of the subjects in the study will receive oral prednisone (**see attached product information**). There is an extremely low risk of an anaphylactic reaction to prednisone. Other potential risks of long-term use of steroids include the following: sodium retention, fluid retention, congestive heart failure in susceptible patients, potassium loss, hypokalemic alkalosis, hypertension, muscle weakness, steroid myopathy, loss of muscle mass, osteoporosis, tendon rupture, vertebral compression fractures, aseptic necrosis of femoral and humeral heads, pathologic fracture of long bones, peptic ulcer with possible perforation and hemorrhage, pancreatitis, abdominal distention, ulcerative esophagitis, impaired wound healing, thin fragile skin, petechiae, ecchymoses, facial erythema, increased sweating, may suppress reactions to skin tests, convulsions, increased intracranial pressure with papilledema, vertigo, headache, menstrual irregularities, development of cushingoid state, secondary adrenocortical and pituitary unresponsiveness, decreased carbohydrate tolerance, increased requirements for insulin or oral hypoglycemic agents in diabetics, posterior subcapsular cataracts, increased intraocular pressure, glaucoma, exophthalmos, and negative nitrogen balance due to protein catabolism. The exclusion criteria, relative low dosage and short duration of the intake of prednisone that is used in this project will minimize possible risks.

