Each data will be analyzed separately and presented descriptively as a mean and standard deviation. Furthermore, each variable will be subjected to independent two-tailed t-tests to determine statistically-significant differences between the two experimental arms. Given the diversity of outcomes and the fact that they are largely independent, there does not appear to be the need to perform a Bonferroni adjustment to avoid Type I error. However, the data will be scrupulously analyzed and if evidence of Type I error is observed, such an adjustment will be made.

Timeline.

It is anticipated that the project will take approximately 12 months to complete. We estimate that recruitment and treatment will take place in 11 months and that there will be a 1-month period of data analysis.

Research Staff.

The following are the research staff for this study and their roles:

[name], Director, NYU Voice Center, Associate Professor, Dept. of Otolaryngology – will perform videostroboscopy and he has expertise in the diagnosis and management of vocal pathology.

[name], Assistant Professor, Dept. of Otolaryngology – will collect voice recordings and aerodynamic measures and has expertise in voice evaluation and conducting voice research.

[name], MA, CCC-SLP, Rusk Institute of Rehabilitation – will provide voice therapy. She is a voice pathologist and specialist in the rehabilitation of the injured voice.

[name] MD, NYU Voice Center – will be the study coordinator. He is a research associate and has expertise in conducting voice related research.

Facilities.

The research will be conducted at the clinical offices of [name] (PI), located at [name] and at Rusk Rehabilitation Outpatients Services, ACC- [name]. The offices have the necessary equipment, personnel, and computer hardware/software for conducting the study.

Limitations.

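### Dropouts are replaced and no analysis set is stated, so the primary t-test would most likely omit randomised subjects without a final VHI-10, although VHI-10 scores that could keep them in are already collected

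*Combined protocol and SAP*

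**What the plan says.** Under (c) Approach, Subjects and Protocol, twenty envelopes are prepared per arm, and "Replacement envelopes will be added if/when subjects drop out from the study". The arm of a replacement envelope, the definition of a dropout and any follow-up of dropouts are not given.

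The same section ties the last assessment to the end of treatment, with no fixed week: "At the completion of therapy, subjects will follow-up with the treating physician". Under Dependent Variables and Data Collection, "VHI-10 data will be collected during the initial, interval, and final evaluations". Figure 3 defines the primary variable as the VHI-10 change from before to after treatment.

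Other VHI-10 scores exist. "During therapy, subjects will be asked to fill out VHI-10 forms on a bi-weekly basis", and "These forms will be collected for study purposes". Of the instrument itself the protocol says "It is administered routinely as a component of clinical care at the NYU Voice Center", with completed forms scanned into the medical record.

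For the analysis, Sample Size and Statistical Considerations says that "each variable will be subjected to independent two-tailed t-tests to determine statistically-significant differences between the two experimental arms". Data Analysis lists comparisons among the initial, interval and final evaluations only. Neither section names an analysis set, a rule for a missing score or a use for the bi-weekly forms.

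**The concern.** A t-test on change needs a baseline and a final value. With no other rule, a subject who leaves therapy early contributes nothing to the primary comparison, and the replacement fills the place. The result is a comparison of completers rather than of the groups that were randomised.

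Adding replacements causes no bias in itself. Leaving out the dropouts can, if leaving is related to response and either the loss rate or the direction or strength of that relation differs by arm. Equal loss rates are safe only if selection has the same direction and strength in both arms.

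The plan supplies a reason to expect unequal loss. Specific Aims predicts for the steroid arm "more rapid improvement, the necessity for fewer voice therapy sessions, and a more global voice improvement". If that is right and dropout depends on response, one common dropout rule already removes different fractions of the two arms. With about 20 subjects per arm, a few exclusions matter, and without a written rule the decision on whom to include can be made after scores are known.

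**Working it through.** **Inputs.** From Sample Size and Statistical Considerations: mean change 14 (steroid) and 10 (placebo), so a difference of 4; SD 7; 20 per group. The 33% given there is screen failure, not dropout. The plan has no dropout figure, so every dropout input below is an assumption. The 20 per group is taken as given; whether it follows from its own inputs is a separate question.

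**Model.** Let Z be the standardised score that drives dropout, with correlation r to the final change (r = 1 if the final change itself drives it, 0.5-0.8 for an early score). The probability of leaving is probit in Z with slope b, from 0.5 (mild) to 1.5 (strong). Put c = b/√(1+b²), which is 0.447 for b = 0.5 and 0.832 for b = 1.5. If a fraction p of an arm is lost, the completers' mean moves by

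shift = 7 · r · c · λ(p), where λ(p) = φ(Φ⁻¹(p))/(1−p).

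λ(0.20) = 0.350, λ(0.10) = 0.195, λ(0) = 0.

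**No true effect, same direction and strength of selection.** Bias = 7 · r · c · [λ(p₁) − λ(p₂)].

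| Loss by arm | Mildest (b 0.5, r 0.5) | Strongest (b 1.5, r 1) | Type I error |
|---|---|---|---|
| 20% vs 10% | 7·0.5·0.447·0.155 = 0.24 | 7·1·0.832·0.155 = 0.90 | about 5-8% |
| 20% vs 0% | 7·0.5·0.447·0.350 = 0.55 | 7·1·0.832·0.350 = 2.04 | about 5.5-16% |
| 20% vs 20% | 0 | 0 | 5% |

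The error rates come from simulating the completer t-test with 20 completers per arm. As a cross-check, the shift in an arm equals p times the gap between completers and dropouts. At 20% loss the gaps are 2.7 and 10.2 points, and 0.2 × 2.7 = 0.54 and 0.2 × 10.2 = 2.04.

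**Equal loss, opposite selection.** If 20% leave each arm, but poor responders leave one and good responders the other, the shifts add: 2 × 0.55 = 1.1 up to 2 × 2.04 = 4.1 points.

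**The plan's 4-point effect, one common rule, 20% lost overall.** The driving score differs between arms by d, so the two probit quantiles differ by c·d/7.

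- Final change drives dropout (d = 4). For b = 0.5, losses are 16.5% and 23.5%, and the difference is 4 − 7·0.447·(0.4025 − 0.2965) = 3.67. For b = 1.5, losses are 13.5% and 26.5%, and it is 4 − 7·0.832·(0.4457 − 0.2509) = 2.87.
- An early score with SD 7 that carries half the effect drives dropout (d = 2, r 0.5-0.8). For b = 0.5, losses are 18% and 22%, and the difference is 3.87-3.92. For b = 1.5, losses are 17% and 23%, and it is 3.54-3.71.

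The shrinkage is the same whether poor or good responders leave.

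**How far a model helps.** A baseline-adjusted repeated-measures model (compound symmetry, all randomised subjects) was simulated with 2,400 replicates. It used interval, four bi-weekly and final scores; four is an assumption. When an observed score drove dropout, bias was at most 0.11 points. When the final change drove it, bias fell from 0.53 to 0.31, 0.93 to 0.46, 1.04 to 0.50 and 2.01 to 0.97, so by about half. Unequal numbers of bi-weekly forms were not simulated.

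**Numbers randomised.** For 20 completers per arm: 20/0.8 + 20 = 45 at 20% versus 0% loss, and 20/0.8 + 20/0.9 ≈ 47 at 20% versus 10%. If replacement envelopes were instead drawn 1:1 at random until 40 complete, the split would average 40·0.8/1.8 = 17.8 versus 22.2, or 40·0.8/1.7 = 18.8 versus 21.2.

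**The case against.** The strongest reply is that the likely harm is modest and rests wholly on assumed dropout. At 20 per arm the standard error of the difference is 7·√(2/20) = 2.2 points, so 0.2-0.9 points is at most 0.4 of a standard error. The one mechanism tied to the plan's own text, a common rule with a drug that works, pulls the estimate towards zero. The inclusion criteria require willingness to take part in therapy, the drug course lasts four days, and the final visit is routine care, so 20% versus 0% is not an expected outcome. All of this stands, and it limits the size of the point. It does not supply the missing analysis set.

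A second reply is that routine clinic scores in the medical record may cover some who stop. This also stands, but the plan does not say that they would be used.

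A third is that the proposed model is only partly tested. Therapy has no fixed length and is expected to be shorter with steroid, so the number of bi-weekly forms may differ by arm, and the end of therapy has no date for someone who stops. That is correct, and the fix asks for both to be settled.

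A reader might go further and infer that the plan adopts a completer analysis, that replacement in itself breaks randomisation, or that a false positive is likely. The documents support none of these. Exclusion is an inference from silence, replacement is harmless if dropouts stay in the analysis, and a materially raised type I error needs loss or selection that differs by arm without a true effect, for which the plan gives no evidence.

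**Conclusion.** The point holds in a limited form and should be acted on. Followed as written, the plan most likely leaves randomised subjects without a final score out of the primary test. The resulting bias is uncertain in size and, if selection is specific to an arm, in direction.

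Under the assumptions shown, a true 4-point difference would be estimated at roughly 2.9-3.9 points. With no true effect, a spurious difference of 0.2-0.9 points is plausible, and 0.5-2.0 is a stress case. Equal loss with opposite selection could give 1.1-4.1 points, so equal rates alone are no reassurance. Confidence is medium: the omission is plain in the text, while the magnitude depends on dropout inputs that the plan does not give.

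**What to change.** - State that all randomised subjects are analysed in their assigned arm, that replacements are added to dropouts and never substituted for them, and which arm a replacement envelope carries.
- Ask subjects who stop therapy, but have not withdrawn consent, for a VHI-10 form, and use routine clinic scores where they exist.
- Replace the t-test on VHI-10 change with a baseline-adjusted analysis, either a repeated-measures model or multiple imputation, that uses the interval, bi-weekly and final scores already collected.
- State what the end-of-therapy target means for a subject who stops, and how unequal numbers of bi-weekly forms are handled.
- Report losses by arm and by stage: before the interval visit, before therapy, during therapy.
- Add a sensitivity analysis that shifts dropouts' values by a range of amounts, separately by arm, because the model only partly corrects dropout that depends on unobserved scores.

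The cost is protocol and analysis wording, one form from each subject who stops, and a little more analysis work. The analysed number rises from 40 to about 45-47 in the cases above. Treatment and visits do not change.
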